### **Overall Design:**

This is a multicenter, open-label study to assess the safety and tolerability of long-term use of 75 mg rimegepant ODT, dosed as PRN, taken up to one tablet per calendar day, in Chinese participants with migraine.

The Screening phase includes a Screening Visit and a 30-day Observation Period (OP). For participants to be eligible for the study, they must have 6-18 migraine attacks of moderate to severe intensity per month in the 3 months prior to the Screening Visit.

Upon the completion of the Screening Visit, participants will be provided an electronic diary (eDiary) to document each day of the 30-day Observation Period if a migraine occurs, the intensity of each migraine attack and if the migraine is treated. Participants will record the standard of care migraine treatment received on a personal device APP (BYOD, Bring Your Own Device). After the completion of the 30-day OP, participants will return to the clinic for the Baseline Visit. At the Baseline Visit, eligibility for the continuing participation in the study will be assessed before study medication is dispensed. Participants need have at least 6 migraine days during the 30-day OP to be eligible and women of childbearing potential (WOCBP) must have a negative pregnancy test result prior to dispensing study drug. After the investigator reviews the results of the baseline laboratory assessments and determines the participant's eligibility, the site staff will inform the participant whether or not he/she is eligible to start dosing in the Long-Term Treatment Phase (LTT). The eligible participants will be instructed that they can take a maximum of one tablet of rimegepant per calendar day during the 52-week Long-Term Treatment Phase at the onset of a migraine (of mild to severe intensity).

Participants are required to record their migraine occurrence and severity via eDiary, and all study medication dose and standard of care migraine treatment taken via BYOD. Participants will also use BYOD to complete the Preference of Medication (PoM) questionnaire and the Satisfaction with Medication (SM) questionnaire at specified study visits.

At select study visits, participants will complete or will be administered the Migraine-specified Quality-of-Life Questionnaire v 2.1 (MQoLQ), the Migraine Disability Assessment (MIDAS), and Clinical Global Impression-change (CGI-c) scale in the paper scales provided by study site.

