A multicenter open-label, long-term study (BHV3000-201) was conducted to evaluate the safety and tolerability of rimegepant 75 mg tablet taken as needed (up to 1 tablet per day upon onset of a migraine of mild, moderate, or severe intensity) for the acute treatment of migraine for up to 52 weeks. This multiple-dose, long-term study of rimegepant 75 mg administered for up to 52 weeks confirmed the favorable safety profile across a variety of safety endpoints, including AE assessments, clinical laboratory testing including LFTs, vital signs and ECGs. Safety data from the double-blind treatment and the open-label extension phases of the pivotal Phase 2/3, randomized, double-blind, placebo-controlled preventive treatment of migraine study (BHV3000-305) support a favorable safety profile of rimegepant 75 mg administered EOD for the preventive treatment of migraine. Rimegepant 75 mg administered EOD + PRN for up to 52 weeks in the open-label phase is well tolerated, with no new safety signals observed in the open-label-extension phase. It is not known if it is safe to take more than 18 doses of rimegepant in 30 days. Taking into account the measures to minimize risk to participants with episodic migraine, the potential risks associated with rimegepant are justified by the anticipated benefits that may be afforded to participants with daily dosing regimens.

There are no adequate data on the developmental risk associated with the use of rimegepant in pregnant women. Women of childbearing potential (WOCBP) must have a negative pregnancy test and WOCBP must use an acceptable method of contraception to avoid pregnancy throughout the study in such a manner that the risk of pregnancy is minimized. Participants undergo regular pregnancy testing throughout the duration of the study. Although no safety issues in clinical trials of rimegepant were observed, cardiovascular events, cerebrovascular events, hypertensive events, and serious gastrointestinal events associated with constipation are reviewed in each aggregate report per FDA request. None of these reviews have detected any safety signal associated with these events. Participants are excluded if there is uncontrolled, unstable, or recently diagnosed cardiovascular disease or hypertension. Participants are monitored through multiple safety endpoints, including AE assessments, clinical laboratory testing, vital signs and ECGs.

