- Return unused study drug for compliance check (at each site visit);
- Return eDiary and review eDiary and BYOD of completion for completeness (at each site visit);

- Daily recording of migraine attacks and their severity by eDiary;
- MSQoLQ Version 2.1 (at Weeks 12, 28, 40, 52, or early termination);
- Migraine PoM for migraine (Week 28 and Week 52 or at early termination);
- Satisfaction with Medication survey (Week 28 and Week 52 or Early Termination);
- CGI-c scale (at Weeks 28 and 52 or early termination);
- MIDAS (at Weeks 12, 28, 40, 52 or early termination).

Upon completion of the Baseline Visit, WOCBP will be provided with urinary pregnancy test kits so that participants can test at home if necessary. When WOCBP participants cannot confirm pregnancy status, a urine pregnancy test must be completed at home before taking study drugs.

During the treatment period, participants have to use the last bottle of study drug before opening a new bottle of study drug. Three wallets of study drug will be dispensed to the participants at each visit of Week 4, Week 8, and Week 12. Study drug will be dispensed at Week 16, Week 28, Week 40 visits as needed, the maximum dispensing limit for each visit is 7 bottles per participant. Study drug will be dispensed at site visits as needed. Dispensing of study drug may also occur at unscheduled visits as needed.

If a participant lacks 6 or more diary reports per month for 2 months (continuous or non-continuous), the participant's continued participation in the study should be terminated due to lack of compliance.

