## 5.5. Prophylactic and Standard of Care Migraine Medications

Participants using prophylactic migraine medications are permitted to remain on therapy if the dose has been stable for at least 2 months prior to the Baseline Visit and this dose is not expected to change during the study. Participants who previously discontinued prophylactic migraine medication must have done so at least 5 half-lives of the prophylactic medication prior to the Screening Visit.

Participants may need to take previously prescribed standard of care medications: aspirin, ibuprofen, acetaminophen (including Excedrin®Migraine) up to 1000 mg/day for a maximum of 2 consecutive days at a time, naproxen (or any other type of non-steroidal anti-inflammatory [NSAID]), antiemetics (eg, metoclopramide or promethazine), or muscle relaxants, which are used during the study (Observation Period and Long-Term Treatment Phase) for the standard of care treatment of migraine.

Use of triptans by participants without a contraindication to their use is allowed during the Observation Phase but must be discontinued at the Baseline Visit. As described above, use of triptans is prohibited during the Long-Term Treatment Phase. With the exception of triptans described in this section, participants are allowed to take standard treatment for migraine during the study, if needed, but are required to meet dose restrictions if taking acetaminophen (no more than 1000 mg/day at a time for 2 consecutive days).

If a participant takes a tablet of study drug and experiences a migraine later that day, the participant can take standard of care medications for migraine (as described in this section above) after taking the study drug that day. Participants are not allowed to take more than 1 tablet of the study medication per calendar day.

Use of standard of care medications during Observation Period and Long-Term Treatment Phase, will be recorded by the participant via BYOD and reported to the site.

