7.2.5 Analysis Visit Windows

According to Section 4.3 of the protocol, the analysis visit windows for efficacy analyses will be defined. Analysis windows for the secondary endpoint will be defined within the OP and LT_T analysis periods that are defined in Section 7.2.4 (See [Table 2](#)[Table 2](#)). The calculation of number of migraine days will be based on the study day as defined in Section [Error! Reference source not found.](#)[7.2.3](#). Analysis windows for the exploratory endpoints will be defined directly as below in [Table 3](#)[Table 3](#).

Table 2. Analysis Windows for Migraine Days

Per 4-week Interval	Analysis Window in the LT _T Analysis Period (Study Day)
Month 1: Week 1 to Week 4	1-28

Month 2: Week 5 to Week 8	29-56
Month 3: Week 9 to Week 12	57-84
Month 4: Week 13 to Week 16	85-112
Month 5: Week 17 to Week 20	113-140
Month 6: Week 21 to Week 24	141-168
Month 7: Week 25 to Week 28	169-196
Month 8: Week 29 to Week 32	197-224
Month 9: Week 33 to Week 36	225-252
Month 10: Week 37 to Week 40	253-280
Month 11: Week 41 to Week 44	281-308
Month 12: Week 45 to Week 48	309-336
Month 13: Week 49 to Week 52	337-end of LTT

Table 3. Analysis Windows for MSQoLQ, MIDAS, PoM, SM, and CGI-c Scale

Scheduled Visits *	Target Day (Based on Study Day)	Analysis Window (Study Day)
Baseline	1	Prior to or on the first dose date
Week 12	84	71-98 #
Week 28	196	183-210 #
Week 40	280	267-294 #
Week 52	364	351- end of LTT
Early Termination	The Early Termination Visit or last post-baseline questionnaire from the early terminated participants	

* The PoM, SM, and CGI-c scale will not be collected at baseline, Week 12 and Week 40.

For early terminated participants, the Week X window end date will be the minimum of (1) Early Termination Date -1 day or (2) Week X analysis window end date, where X is the last Week with Target Day being prior to Early Termination Date.

In [Error! Reference source not found.](#)[Table 3](#), if there are multiple non-missing values fall into a same analysis windows, then the following algorithm will be taken to identify the value for analysis:

1. The value closest to the target day for the visit will be used.
2. If the observations are with equal distance from the target day in absolute value, the one with correct nominal visit label will be used. For example, if two observations fall into the analysis window for Week 28 Visit on Study Days 190 and 202, respectively, the observation that is recorded as Week 28 will be used.

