7.5.1 Drug Exposure

Drug administration data collected via CRF will be used to summarize drug exposure as follows:

- Time in the OP (weeks) = (OP end date – OP start date + 1)/7
- Time in the LTT period (weeks) = (LT^T analysis period end date – LT^T analysis period start date + 1)/7
- Time on rimegepant exposure (weeks) = (study drug end date – study drug start date + 1)/7
- Cumulative administered rimegepant dose (tablets) = sum of doses administered on the drug management page of CRF.
- Average administered rimegepant dose during the LTT period (tablets per month) = 4 (weeks)*cumulative administered dose (tablets) / Time in the LTT period (weeks) if time in the LTT period \geq 2 weeks; = cumulative administered dose if time in the LTT period $<$ 2 weeks.

In the above drug exposure summary, descriptive statistics of n, mean, standard deviation, median, 25th and 75th percentiles, minimum and maximum will be presented.

- For the average rimegepant exposure during the LTT period (tablets per month), the number and percentage of participants will be summarized by < 2, \geq 2 to < 8, \geq 8 < 14, < 14 and \geq 14 tablets per month.
- The number and percentage of participants taking > 1 tablet per day (i.e., actual dose of “other”). It will be calculated based on the study drug administration CRF.

In addition, rimegepant exposure during the LTT period will be summarized by the average Rimegepant exposure categories and total for each month (i.e., 4-week interval) as defined in [Table 2](#). The rimegepant exposure (tablets) for each month will be determined as follows:

- rimegepant exposure (tablets) for Month X = sum of doses administered on the drug management page of CRF within the Month X window, where X=1, 2, 3, 4, 5, 6, 7, 8, 9, 10, 11, 12.

- Rimegepant exposure (tablets) for Month 13 = sum of doses administered on the drug management page of CRF within the Month 13 window if exposure \leq 28 days; = sum of doses administered on the drug management page of CRF within the Month 13 window *28/exposure days if exposure $>$ 28 days.

Participant's exposure to the study drug will be listed in detail.

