7.5.2 Adverse Events

The AEs will be coded by the latest version of MedDRA. The toxicity of AEs will be graded using National Cancer Institute Common Terminology for Adverse Events (NCI CTCAE) v5.0.

All AEs will be categorized according to the safety analysis periods (refer to Section 7.2.4), ie. pre-treatment safety period, treatment safety period, and follow-up safety period:

- Pre-treatment AEs, ie, those with imputed AE onset dates falling within the pre-treatment safety period.
- Treatment-emergent adverse event (TEAEs), ie, those with imputed AE onset dates falling within the treatment safety period. See Section 7.2.1 for AE onset date imputation.
- Follow-up AEs, i.e., those with imputed AE onset dates falling within the follow-up safety period.

Drug-related AEs are the AEs assessed by the site investigator as having a relationship to the investigational product of "definitely related", "probably related", or "possibly related".

An overall summary of AEs will display the number and percentage of participants reporting the following AEs for participants in different categories of average rimegepant exposure (< 2 , ≥ 2 to < 8 , ≥ 8 to < 14 , < 14 and ≥ 14 tablets per month) and overall participants for treatment safety and follow-up safety analysis periods, respectively, as below:

- For treatment safety analysis period, the following will be summarized using SS:
 - Any TEAE, any drug-related TEAE,
 - Any serious TEAE, any drug-related serious TEAE,
 - Any TEAE with CTCAE grade ≥ 3 , any drug-related TEAE with CTCAE grade ≥ 3 ,
 - Any TEAE leading to drug interruption; any drug-related TEAE leading to drug interruption,
 - Any TEAE leading to treatment discontinuation, any drug-related TEAE leading to treatment discontinuation,
 - Any TEAE leading to study discontinuation, any drug-related TEAE leading to study discontinuation,
 - Any TEAE leading to death, any drug-related TEAE leading to death.

- For follow-up safety analysis period, the following will be summarized using FUSS:
 - Any AE,
 - Any SAE,
 - Any AE leading to death.

Further, the number and percentage of participants with the following AEs will be tabulated by SOC and PT for participants in different categories of average rimegepant exposure (< 2 , ≥ 2 to < 8 , ≥ 8 to < 14 , < 14 and ≥ 14 tablets per month) and overall participants for treatment safety and follow-up safety analysis periods, respectively, as below:

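### SAP 7.5.1 scales Month 13 tablets to 28 days only when the window is long (a minor error); separately, a count of participants above 18 doses in any 30 days would be a cheap addition

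*SAP*

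**What the plan says.** **Month 13.** SAP Table 2 (7.2.5) gives Months 1-12 fixed 28-day windows and lets Month 13 run from Study Day 337 to the end of the long-term treatment (LTT) period. SAP 7.5.1 takes raw tablet sums for Months 1-12. For Month 13 it takes the "sum of doses administered on the drug management page of CRF within the Month 13 window if exposure" is at most 28 days, and otherwise multiplies that sum by 28 over exposure days. Exposure days are not defined. In the same section the whole-LTT average is "4 (weeks)*cumulative administered dose (tablets) / Time in the LTT period (weeks) if time in the LTT period" is at least 2 weeks, which scales in both directions.

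**End of treatment.** SAP Table 3, in the column that begins "Target Day (Based on Study Day", puts Week 52 at Day 364. The visit window is ±7 days in Protocol Table 1 and Section 4.3.3, but ±3 days in Protocol 4.3.2.

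**High use.** Protocol 2.5 states: "It is not known if it is safe to take more than 18 doses of rimegepant in 30 days". The synopsis says participants will be told "they can take a maximum of one tablet of rimegepant per calendar day during the 52-week Long-Term Treatment Phase". SAP 7.5.1 classes participants by whole-LTT average: <2, 2 to <8, 8 to <14, <14 and ≥14 tablets per month. The adverse event tables in SAP 7.5.2 are "for participants in different categories of average rimegepant exposure", and the same classes split the by-exposure laboratory, liver function, vital sign and ECG tables in 7.5.3 to 7.5.5. The one over-use count planned is of participants taking more than one tablet in a day. Quartiles, maxima, a monthly exposure summary and a participant listing are also planned.

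**The concern.** The Month 13 rule corrects only one of the two ways in which an open-ended window can differ from 28 days. A reader comparing 13 monthly rows could see use fall at the end of the year when nothing had changed except the visit date.

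The second matter bears on the primary objective, the long-term safety of as-needed use up to one tablet per day. The protocol names a range of use whose safety is unknown, and the dosing rule allows participants to reach it. The exposure classes do not isolate that range, so the report would not state how many participants entered it or which events followed. A reader would have to rebuild this from the listings.

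**Working it through.** The plan gives no expected figure for monthly exposure. Its only numerical safety justification (Protocol 10.2, SAP 3.4) reproduces and is not in dispute: 1 − 0.99^240 = 91.0% and 1 − 0.95^240 > 99.9%.

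**Month 13**

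Window length is L = end-of-treatment day − 336. With a constant rate of use, the SAP figure divided by the true 28-day figure is min(L, 28)/28.

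Single participants:
- Ending on Day 357: L = 21 and 21/28 = 0.75, so 25% low. A true rate of 14 per 28 days shows as 10.5.
- Ending on Day 371: L = 35, scaled by 28/35, no bias.
- Terminating early on Day 350: L = 14, so 50% low.

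Averages, assuming end-of-treatment dates are spread evenly over whole days:

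| Visit window | Days | Mean of min(L, 28) | Bias | Share with L < 28 |
|---|---|---|---|---|
| 364 ± 7 | 357-371 | 392/15 = 26.13 | −6.7% | 7/15 = 47% |
| 364 ± 3 | 361-367 | 190/7 = 27.14 | −3.1% | 3/7 = 43% |
| 365 ± 7 | 358-372 | 399/15 = 26.60 | −5.0% | 6/15 = 40% |
| 365 ± 3 | 362-368 | 193/7 = 27.57 | −1.5% | 2/7 = 29% |

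Day 365 is included because 52 full weeks counted from Day 1 end there, one day after the SAP target.

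Partial Months 1-12 are also unscaled, but matter less. If the 12% dropout in Protocol 10.2 is spread evenly over 13 months, 0.12/13 = 0.92% of participants leave in each month and lose half a month on average, which is about 0.5% per row.

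**High use**

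- 18 doses in 30 days equals 18 × 28/30 = 16.8 per 28 days.
- The SAP cut of 14 per 28 days equals 14 × 30/28 = 15 per 30 days. The ≥14 class therefore mixes users at 14 to 16.8 per 28 days with users above 16.8.
- Averaging can also move participants with high-use months into lower classes:
  - 6 months at 20 tablets and 7 at 8: (120 + 56)/13 = 13.5, class 8 to <14.
  - 3 months at 24 and 10 at 8: (72 + 80)/13 = 11.7, class 8 to <14.
  - 1 month at 28 and 12 at 4: (28 + 48)/13 = 5.8, class 2 to <8.
- The monthly table uses fixed 28-day windows, so a 30-day span that straddles two months can exceed 18 without either month doing so.

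**The case against.** **On Month 13.** The SAP labels the monthly variable in tablets, not tablets per month, and leaves Months 1-12 as raw sums. Month 13 could be meant as tablets within at most 28 days, and then nothing is biased. It is true that the bias exists only when the row is read as a 4-week figure. But multiplying long windows by 28/exposure days is a rate adjustment, which shows that a 28-day scale was intended. A row that mixes scaled and unscaled values is on neither scale. It is also fair that LTT ends at the later of the end-of-treatment visit and the last dose, so some windows will be slightly longer than assumed here.

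**On high use.** The sentence in Protocol 2.5 is benefit-risk background. No objective or endpoint makes 18 doses in 30 days a question for this trial, and a whole-period average is a reasonable metric for long-term safety. Protocol 10.3 has exposure and safety data reviewed continuously, and Protocol 7.4 has investigators assess overuse. All of this stands, and it is why the extra table is an improvement rather than the repair of an error. Those provisions concern monitoring, however, and do not produce a reported count.

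A reader might infer that no table ties events to heavy use at all. The documents do not support that. Anyone averaging above 16.8 tablets per 28 days falls in the ≥14 class, whose events are tabulated, and the planned maxima would reveal some heavy months.

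**Conclusion.** **Month 13** is a small error as written. The average shortfall is 1.5% to 6.7% under evenly spread end-of-treatment dates and a constant rate of use; it is 25% for an end on Day 357. It is confined to the Month 13 row of the monthly exposure table. A reader might infer that the exposure classes, and so the safety tables, are distorted. They are not, because the whole-LTT average divides by actual time.

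**The high-use count** is an optional, low-cost addition. What holds is narrow: no planned table counts participants above 18 doses in any 30 days or separates their events from those of other participants.

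A reader might also infer from the migraine frequencies in Protocol 10.2 that many participants would exceed the threshold. The documents do not allow an estimate. Any day with study drug counts as a migraine day (Protocol Appendix 2), so migraine days are only a ceiling on tablet days. Tablets per migraine day are not given, and "participants are allowed to take standard treatment for migraine during the study, if needed". The correlation of use from month to month is not given either. The supply rule does not settle it, because wallet size is not stated and "Dispensing of study drug may also occur at unscheduled visits as needed".

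**What to change.** In SAP 7.5.1:

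1. For Month 13 use 28 × doses / LTT days in the window, whether the window is shorter or longer than 28 days. Define exposure days as LTT days in the window. Require at least 14 LTT days, in line with the 2-week rule for the LTT average, and show how many participants are left out. Apply the same rule to partial Months 1-12 so that all rows share one scale.
2. Add the number and percentage of participants with more than 18 doses in any 30-day window. For them, give descriptive counts of any TEAE, any serious TEAE and liver function elevations. Show those from the 19th dose to the end of the qualifying window or windows separately from those later in the treatment safety period. Starting at the 19th dose leaves out events that came before the threshold. The split keeps later months of ordinary use from being read as heavy use.

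The cost is one changed derivation, a rolling 30-day count and one small table, all from data already collected. The downsides are small or empty cells, a self-selected group, and sparse liver sampling after Week 16 (every 12 weeks), so the table supports description only. No dosing limit is proposed.

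Separately, the ±3 days for the Week 52 visit in Protocol 4.3.2 must be reconciled with the ±7 days in Protocol Table 1 and Section 4.3.3.
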